3 STUDY ENDPOINTS

- Primary 1: Subjective questionnaires of product evaluation (Duke Sensory Scale, Product Evaluation Scale, Drug Effects, Hedonic Attribute), withdrawal (MNWS, QSU-B, PANAS), and readiness to quit (contemplation ladder).
- Primary 2: Number of cigarettes smoked per week during the field period.
- Secondary: Awareness and beliefs about filter ventilation and perceptions of messaging.
- Secondary: Exhaled CO is defined as level of CO measured in exhaled breath after a 15 s breathhold. This is typically 10ppm or above in daily smokers and <3 ppm in nonsmokers.
- Secondary: Smoking topography as assessed by particulate matter retained on used filters.

Roswell Park Protocol Number: I 757820

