5 STUDY TIMELINES

5.1 Duration of an Individual Subject's Participation in the Study

The proposed study consists of multiple videoconferencing sessions (a total of 3) throughout a 2-week field study. Following informed consent, participants will be randomly assigned to 1 of 4 message conditions and use the assigned product for 2 weeks. This 2-week field study involves participants logging their use of tobacco products, while the weekly videoconferencing sessions involve additional questionnaires and guidance about field data collection.

Roswell Park Protocol Number: I 757820

	Data Collection Sessions (Weekly)			Field (Daily for 14 days)
	Video 1	Video 2	Video 3	Ecological Momentary Assessment
Tobacco Use Behavior				
Cigarettes per Day	X	X	X	X
Other Tobacco Use	X	X	X	X
Context of Use (e.g., location)				X
Questionnaires				
Message Perceptions (response, health risk, purchase)	X All messages	X Randomly Assigned Message	X Randomly Assigned Message	
Vent Awareness	X	X	X	
Product Evaluation (Duke Sensory, Product Evaluation Scale, Drug Effects, Hedonic Attribute)	X	X	X	X Select Items
Readiness to Quit (Contemplation Ladder)	X	X	X	
Withdrawal (MNWS, QSU-B, PANAS)				X Select Items
Attention to Messaging				X
Biomarkers				
Exhaled CO				X
Topography via Filter Analysis				X

Estimated date for the investigators to complete this study

Data collection should be completed by 12/31/2022.

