11.4 Data To Be Collected

- **Baseline measures and covariates will assess:**
 - Demographics (age, sex, race/ethnicity, education, income)

Roswell Park Protocol Number: I 757820

- Tobacco use behaviors (consumption, brand, menthol preference, past quit attempts)
- Delay discounting
- A series of previously used items will assess knowledge and perceptions of filter vents.^{113,117}
- Nicotine dependence will be assessed using:
 - Fagerström Test for Nicotine Dependence (FTND¹¹⁸)
 - PROMIS

Behavioral aspects of cigarette dependence will be assessed using:

- The Glover-Nilsson scale^{120,121}
- The different scales are used to capture different dimensions of tobacco dependence.¹²²
- Exhaled air CO will be collected by the participants twice each day using a personal CO monitor provided by the researchers. The CO monitors provided are coVita iCo™ Smokerlyzers®, which are intended for research and consumer use and are compatible with a Smartphone or tablet (iOS or Android).

Perceptions of product messaging: In this study, we are interested in risk perceptions, smoking-related expectancies, and behavioral intentions. We will assess risk perceptions for specific products using a risk ladder.¹²⁹ More generalized perceptions of risk for cancer are captured using the tripartite risk (TRIRISK) measure, which captures deliberative, affective, and experiential components of risk perception.¹³⁰ The adult smoking consequences questionnaire (SCQ) will assess smoking-related expectancies.^{103,131} Behavioral intention is assessed using Juster's consumer purchase probability scale, a widely used marketing metric.¹³²⁻¹³⁴ Additional questions will include responses to messaging (e.g., message was powerful, memorable).

Responses to product use will be assessed in a number of ways: Response to nicotine dose will be assessed using the Minnesota Nicotine Withdrawal Scale (symptoms of nicotine withdrawal).¹³⁵ Cigarette craving in field will be assessed using the Brief QSU commonly used in cue reactivity research. Behavioral economic measures will assess product demand. A delay discounting task will assess preference for immediate reward,¹⁴⁸ while purchase tasks will be used to estimate level and elasticity of demand.¹⁴⁹⁻¹⁵¹ Sensory measures will be collected using the Duke Sensory Scale and Hedonic Attribute Scale. Drug effect measures include the Product Evaluation Scale and Drug Effects/Liking Scale.

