Cigarette tracking via EMA: For the field study, the key outcome is the total number of cigarettes smoked. Participants will be asked to complete REDCap questionnaires on their personal phone (iOS or Android). Participants can use the MyCap application to respond to questionnaires. Additionally, REDCap can interface with Twilio, a secure text-messaging platform, to send study related messages and surveys via SMS (text messaging). Proposed EMA methods are based on established best practices. Participants will complete 5 questionnaires every day. These questionnaires will occur at the same time each day: 11am, 1:30pm, 4pm, 6:30pm, and 9pm. These daily reports will be used to assess cigarette and e-cigarette consumption, and 10 items relating to subjective ratings of nicotine withdrawal (e.g., craving, irritability) and mood (e.g., calm/relax, happy). At 11am only, participants will complete selected items from the Hedonic Attribute Profile and Product Evaluation Scale. At 9pm only, participants will be asked to rate the taste, satisfaction,

Roswell Park Protocol Number: I 757820

enjoyment, and craving relief from the cigarettes they smoked that day. Participants will also be asked to take a CO measurement at this time. At the 1:30 and 6:30 prompts, participants will be asked about situational factors related to use (Location, smoking permitted, with others, activity, craving) and complete the Duke Sensory Evaluation scale. Participants also will be asked to take a picture of their research cigarette pack to ensure compliance. Surveys will be open for 1 hour after the scheduled time for completion. Appendix C demonstrates the EMA schedule and the questions asked at each daily report and pseudo-random prompt. Participants can earn up to \$10 for each day of EMA compliance, with compliance being defined as responding to ≥ 4 of 5 daily prompts (up to 14 days, totaling \$140). Studies that used similar methods had $>90\%$ compliance. [189, 190].

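### Primary 1 names the MNWS, QSU-B and PANAS, but the schedule collects only selected 0–100 ratings in the EMA, so the three named scale scores cannot be derived as planned

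*Combined protocol and SAP*

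**What the plan says.** Section 3 defines Primary 1 as a set of questionnaires: four on product evaluation (Duke Sensory, Product Evaluation, Drug Effects, Hedonic Attribute), followed by "withdrawal (MNWS, QSU-B, PANAS" and then the contemplation ladder for readiness to quit.

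Section 11.4 assigns roles to two of the withdrawal scales: "Response to nicotine dose will be assessed using the Minnesota Nicotine Withdrawal Scale (symptoms of nicotine withdrawal", and "Cigarette craving in field will be assessed using the Brief QSU commonly used in cue reactivity research". It gives no time point for the MNWS.

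The schedule table in section 5.1 has a row "Withdrawal (MNWS, QSU-B, PANAS". Its cells for Videos 1, 2 and 3 are empty. The daily EMA cell is marked, with the limit that only selected items are asked.

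In describing the EMA, section 11.4 speaks of "10 items relating to subjective ratings of nicotine withdrawal (e.g., craving, irritability) and mood (e.g., calm/relax, happy". The EMA part of Appendix C lists these ten: craving, irritability, anxiousness/nervousness, difficulty concentrating, stress, boredom, calm/relaxed, happy, alert and enthusiastic, each on a 0–100 visual analogue scale (VAS).

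The full scales are printed elsewhere in Appendix C, but no visit is given for them.

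**The concern.** A primary endpoint should be computable from the data the schedule collects. Here Section 3 names three published scales, one sentence of section 11.4 promises one of them in the field, and the schedule and EMA forms deliver something else. Someone following the plan to the letter would reach the analysis without the item responses needed for an MNWS, QSU-Brief or PANAS score.

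Two things are at stake. First, nothing says what takes the place of the scale scores, so the choice of items, composite and rating time could be made after the data are seen. Second, the schedule shows no withdrawal, craving or mood measure before the study cigarettes are used. Change from baseline could then not be reported for this domain, and the model could not be adjusted for a starting value.

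**Working it through.** The plan states no figure on this point, so the check is a count and a side-by-side reading.

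**1. How much of Primary 1 is affected.** Section 3 names Duke Sensory, Product Evaluation, Drug Effects, Hedonic Attribute, MNWS, QSU-B, PANAS and the contemplation ladder: 4 + 3 + 1 = 8 instruments. The withdrawal group is 3 of 8.

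**2. Where each group is scheduled (section 5.1).**

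| Primary 1 group | Videos 1–3 | Daily EMA |
|---|---|---|
| Product evaluation (4 scales) | all three | selected items |
| Contemplation ladder | all three | none |
| Withdrawal (3 scales) | none | selected items |

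Withdrawal is the only Primary 1 group with no session administration. Section 11.3 agrees. Session 1 lists history, dependence, expectancies, risk, discounting, respiratory symptoms, vent beliefs, message ratings and three product scales for the usual brand. Session 2 lists vent awareness, product evaluation, readiness to quit and message perceptions, and Session 3 repeats Session 2. None of the three scales appears.

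**3. Whether the EMA items can yield the scale scores.** Matching the ten EMA items to the scales printed in Appendix C:

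| Scale | Printed form | Items matched in the EMA | Coverage |
|---|---|---|---|
| MNWS | 15 items, 0–4, past 24 hours | irritability, anxiousness, concentration, craving | 4/15 = 27% |
| PANAS | 10 words, 1–5 | alert, enthusiastic; also nervous, if anxiousness/nervousness is accepted | 2/10 = 20% or 3/10 = 30% |
| QSU-Brief | 10 statements, 1–7 | none as worded | 0/10 |

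Of the five negative PANAS words (afraid, upset, nervous, scared, distressed), at most one is covered. The matched items number six in all (craving, irritability, anxiousness, concentration, alert, enthusiastic). The other 10 − 6 = 4 (stress, bored, calm/relaxed, happy) correspond to no printed item. The response format differs for all ten. A standard score for any of the three scales cannot be built from these data.

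**4. Whether another rule fills the gap.** Section 22.1 gives a scoring rule only for the mCEQ, which Section 3 does not name. It gives none for the EMA ratings. The room for choice is wide. Under the three fixed reports in Appendix C, each item is rated 3 × 14 = 42 times as a momentary rating, plus 14 whole-day ratings at 9 pm. Read literally, section 11.4 puts the ten items at all five daily prompts, which would give 5 × 14 = 70 momentary ratings.

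**5. Measurement before study cigarettes.** Under section 11.3, EMA recording of the assigned product starts once Session 1 ends. With no withdrawal measure in the Session 1 list, the number of scheduled assessments before study cigarettes is 0. The main models in section 22.1 contain terms for message, sex and other tobacco use, with no baseline covariate.

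**The case against.** The strongest reply is that the schedule openly says selected items, so the plan never meant to give whole scales. On that reading Section 3 merely labels the sources of the items. Much of this stands. A reader might infer that the three scales are never administered at all, and the documents do not support that, because the section 5.1 row schedules items from this group every day for 14 days. Craving in particular is covered well beyond one rating: the EMA also asks for whole-day craving, craving before the last cigarette, and two ratings of craving relief. What the reply does not explain is the section 11.4 sentence promising the Brief QSU in the field, or how a primary endpoint is to be scored from adapted items.

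A reader might also infer that a baseline definitely does not exist. That goes too far. Appendix D has an undefined entry for cognitive and affective measures among the baseline questionnaires. Appendix C prints the MNWS ahead of its in-session block and the PANAS and QSU-Brief within it. None of this assigns a scale to a visit, so the documents conflict and the position is unclear.

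Nor does the gap invalidate the trial's comparison. Participants are randomised, so arms can be compared on the EMA ratings without a baseline value. Withdrawal is not part of the aim in section 1.1 or the hypothesis in section 1.2, and the power statement rests on cigarettes per day. The precision lost by having no baseline cannot be sized from the documents, which give no correlation between a starting rating and the later ones.

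**Conclusion.** The point holds in a limited form. Three of the eight Primary 1 instruments are named as scales but scheduled only as adapted single ratings. Those ratings cover 4 of 15 MNWS items, 2–3 of 10 PANAS words and no QSU-Brief item as worded. The named scores cannot be derived from the plan as scheduled, no replacement score is defined, and no measurement before study cigarettes is scheduled for this domain.

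This is a mismatch in endpoint definition that should be corrected. It does not undermine the randomised comparison of the ratings between arms, and it leaves the cigarette-count endpoint untouched. The conclusion assumes that the section 5.1 table and the section 11.3 session lists govern what is collected. If the undefined Appendix D entry in fact includes these scales at Session 1, a baseline may exist for some of them, but the field scores would still be missing.

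**What to change.** Reconcile section 3, the section 5.1 table, section 11.4 and Appendix C in one of two ways, and say what the Appendix D entry contains.

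- **(a) Name what is collected.** Redefine this part of Primary 1 as the EMA withdrawal, craving and mood ratings. The sponsor should fix the scoring rule before data are seen: which items, combined or separate, momentary or whole-day, and over which days. Ask the same ten ratings once before study cigarettes are used. The consent videoconference, which comes before randomisation, is a natural place. Add that value as a covariate to the section 22.1 model, since collecting it alone changes nothing in the analysis. Remove or amend the statement in section 11.4 that the Brief QSU is used in the field.
- **(b) Collect what is named.** Add the three full scales, already printed in Appendix C, to Videos 1–3. Place the Video 1 administration before any study cigarette is used and ahead of the rating of all pack messages.

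The cost is a few minutes of added questionnaire time, plus edits to the text. Under (a), results will not be directly comparable with published full-scale scores. The new name and the scoring rule in (a) need no new data. Only the pre-use rating does.

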4 LOCAL AND STUDY-WIDE NUMBER OF SUBJECTS

4.1 Total Number of Subjects to be Accrued Across All Sites.

We will conduct this study with current cigarette smokers (100 in Buffalo, 100 in Boston, 100 in Charleston) for a total N of 300. We hope to achieve N=240 with complete data. An equal number of males and females will be recruited for the study at each site.

Stratified recruitment scheme for Study 3.1		
	Cigarette Smoker	
Sex	M	F
Overall N	150	150
Buffalo	50	50
Boston	50	50
Charleston	50	50

4.2 Total Number of Subjects to be Accrued Locally

- Buffalo, NY will recruit an n of 100, with a target of 80 complete cases.
- Charleston, SC will recruit an n of 100, with a target of 80 complete cases.
- Boston, MA will recruit an n of 100, with a target of 80 complete cases.

5 STUDY TIMELINES

5.1 Duration of an Individual Subject's Participation in the Study

The proposed study consists of multiple videoconferencing sessions (a total of 3) throughout a 2-week field study. Following informed consent, participants will be randomly assigned to 1 of 4 message conditions and use the assigned product for 2 weeks. This 2-week field study involves participants logging their use of tobacco products, while the weekly videoconferencing sessions involve additional questionnaires and guidance about field data collection.

Roswell Park Protocol Number: I 757820

	Data Collection Sessions (Weekly)			Field (Daily for 14 days)
	Video 1	Video 2	Video 3	Ecological Momentary Assessment
Tobacco Use Behavior				
Cigarettes per Day	X	X	X	X
Other Tobacco Use	X	X	X	X
Context of Use (e.g., location)				X
Questionnaires				
Message Perceptions (response, health risk, purchase)	X All messages	X Randomly Assigned Message	X Randomly Assigned Message	
Vent Awareness	X	X	X	
Product Evaluation (Duke Sensory, Product Evaluation Scale, Drug Effects, Hedonic Attribute)	X	X	X	X Select Items
Readiness to Quit (Contemplation Ladder)	X	X	X	
Withdrawal (MNWS, QSU-B, PANAS)				X Select Items
Attention to Messaging				X
Biomarkers				
Exhaled CO				X
Topography via Filter Analysis				X

Estimated date for the investigators to complete this study

Data collection should be completed by 12/31/2022.

6 SETTING

6.1 Sites or Locations Where Research Will Be Conducted

We will conduct this laboratory study in Buffalo, Charleston, and Boston.

6.1.1 Where Research Team Will Identify and Recruit Potential Subjects

We will recruit for our laboratory study via community contacts, ad postings in local, daily, weekly, and college newspapers, websites such as Craigslist and Facebook, and local tobacco control networks (methods we have previously used to recruit successfully, cf. 71,152,153). In addition, we plan to make arrangements with local shopping centers to allow recruitment of patrons on-site.

6.1.2 Where Research Procedures Will Be Performed

Remote visits will involve participants joining videoconferences in their own homes.

Roswell Park Protocol Number: I 757820

7 INCLUSION AND EXCLUSION CRITERIA

7.1 How Individuals Will Be Screened For Eligibility

We will recruit adult smokers for the study via community contacts, ad postings in local daily, weekly, and college newspapers, websites such as Craigslist and Facebook, and local tobacco control networks (methods we have previously used to recruit successfully, cf. ^{71,152,153}).

Screening methods may involve live telephone interviews, automated telephone screeners (via IVR), and online screening methods where the recruit will complete an eligibility screener online and receive a callback for scheduling pending eligibility.

7.2 Inclusion Criteria

1. Aged 21-69 years old.
2. Currently smoking daily, at least 5 cigarettes per day, for the past year:
 - a. Primarily using factory-made filtered cigarettes.
3. Fair and above self-rated physical health (self-rated).
4. Fair and above self-rated mental health (self-rated).
5. Not planning to quit smoking in the next 30 days.
6. Able to converse, read, and write in English.
7. Access to smartphone (e.g., iPhone, Android) for Ecological Momentary Assessment (EMA) component.
8. Access to a smartphone/tablet/computer with video capabilities and internet access for remote videoconferencing (EMA check-ins).
9. AUDIT-C score <7 (i.e., no problematic alcohol consumption).
10. Cannabis use ≤ 5 days in the past month.
11. No other illegal drug use in the past month (allow for prescriptions).
12. Not pregnant or breastfeeding or planning to become pregnant during the study period.
13. Participant must understand the investigational nature of this study and sign an Independent Ethics Committee/Institutional Review Board approved written informed consent form prior to receiving any study related procedure.

7.3 Exclusion Criteria

1. Age < 21 or > 69 .
2. Using roll-your-own cigarettes or usual brand of cigarettes is unfiltered.
3. Planning to quit smoking in the next 30 days.
4. Not able to converse, read, and write in English.
5. Adults unable to consent.
6. Minors (any persons under age 21).
7. Prisoners.
8. Poor physical health by self-report.
9. Poor mental health by self-report:

Roswell Park Protocol Number: I 757820

- Exclude Dx psychosis, Dx bipolar, K6 score indicating serious psychological distress.
- 10. AUDIT-C score ≥ 7 (i.e. problematic alcohol consumption).
- 11. Cannabis use >5 days in past month.
- 12. Other illegal drug use in past month.
- 13. Pregnant or breastfeeding by self-report.
- 14. No access to smartphone or videoconferencing.

7.4 Inclusion of Women and Minorities

Both men and women and members of all races and ethnic groups are eligible for this study.

7.5 Special Populations

The following populations will be excluded from study participation:

- Cognitively impaired adults/adults with impaired decision-making capacity
- Individuals who are not yet adults (infants, children, teenagers)
- Pregnant Women
- Prisoners

8 LOCAL AND STUDY-WIDE RECRUITMENT METHODS

8.1 When, Where, and How Potential Subjects Will Be Recruited

We will recruit for our laboratory study via community contacts, ad postings in local daily, weekly, and college newspapers, websites such as Craigslist and Facebook, and local tobacco control networks, and lists of prior study participants (methods we have previously used to recruit successfully, cf. ^{71,152,153}).

8.2 Methods That Will Be Used to Identify Potential Subjects

Screening methods may involve live telephone interviews, automated telephone screeners (via IVR), and online screening methods where the recruit will complete an eligibility screener online and receive a callback for scheduling pending eligibility.

Additionally, we plan to implement a chain referral method. This method has been successfully used in other participant-based studies. Here, all participants who complete the study will be given a “coupon book” containing 3 “coupons” (Appendix A), each with a unique code per participant. The participant may give a coupon to a friend/colleague/relative if they choose. The friend, in turn, may voluntarily call in to complete the screener, just as if they saw an ad. Should the friend successfully complete the study and return the coupon, the original participant may earn \$10 per referral (up to a maximum of \$30). A gift code (e.g., Amazon, Target) will be e-mailed upon the close of the entire study, guaranteeing the maximum amount of time to earn the largest monetary reward. Finally, letters (Appendix A) will be mailed to the home address of participants who have previously completed a tobacco-related studies as the one of the three study sites (i.e., Roswell Park Comprehensive Cancer Center, Medical University of South Carolina, and Harvard School of Public Health) and gave consent to be contacted in the future for other research opportunities.

Roswell Park Protocol Number: I 757820

8.3 Materials That Will Be Used to Recruit Subjects

Ad and chain referral materials included (Appendix A).

8.4 Amount and Timing of Any Payments to Subjects

Participants receive \$50 for each videoconference session (three total). Payment will be in the form of a gift code (e.g., Amazon, Target). Participants can earn up to \$10 for each day of EMA compliance (up to 14 days, totaling \$140), which will be paid by check at the end of the study. Total potential compensation is \$290.

9 CONSENT PROCESS

9.1 Indication of Obtaining Consent

An initial videoconferencing session will be used for informed consent. Consent will be obtained through the REDCap (Research Electronic Data Capture) system used for data collection. REDCap is a secure web-based application that supports data capture and management for research studies. The Investigator and Research Associate will design the study specific consent and upload the most recent CRS versions to the REDCap system. A secure link will be sent to each participant prior to the start time of the study. Research staff will guide the participant form, provide time to read the consent, and answer any questions. Participants and staff will be able to electronically sign, data, and submit the consent in real-time. Once the consent is submitted, it is automatically saved on RPCI protected servers. Access to this folder is restricted to authorized users. Standard protocols for data encryption (via Credant) when using laptops and USB drives will be followed.

In the event of REDCAP being inaccessible for a study visit, .pdf files or paper copies of the consent will be provided to the participants and the participants will be able to sign and return or submit a photo of the signed copy.

